4.3.2 Prostate cancer

- Chemotherapy (not including androgen deprivation therapy), immunotherapy, biologic therapy, radiation therapy, or other investigational product within 4 weeks prior to study entry or likely to be required during the 4-week on-study period
- Patients using corticosteroids or immunosuppressive agents: low dose oral corticosteroids for concomitant medical conditions are permitted. Inhaled or topical corticosteroids are permitted.
- Patients with active infections requiring antibiotics, with bleeding disorders or with other serious illness
- Patients with a concurrent active serious medical condition likely to affect participation in the study, such as a documented myocardial infarction ≤3 months prior or to screening or unstable angina pectoris
- Men who are unwilling to utilize a medically acceptable method of contraception
- Patients unable to sign informed consent or unwilling to comply with the procedural requirements of this clinical protocol.

4.4 TAG-72 Screening

Because PEG-AVP0458 is an antibody fragment specific for TAG-72, only patients with tumours positive for this antigen will be enrolled in the clinical trial. TAG-72 presence in archived tumour specimens will be evaluated using a validated immunohistochemical (IHC) method by TissuPath. Relevant controls will be run in each assay.

Tumours will be defined as TAG-72 positive if at least 20% of tumour cells are stained by IHC (either strongly or weakly).

Clinical investigators or referring physicians from clinical trial sites or CTA member hospitals respectively will obtain written informed consent from the patients under consideration for participation in this study, and arrange for archived tumour specimens to be sent from the relevant hospital department of pathology to the central laboratory (TissuPath) for TAG-72 screening. TissuPath will send results of the TAG-72 screening test to the clinical investigator or referring physician. If the results are positive, the referring physician from a CTA-member hospital will refer the patient to the appropriate clinical trial site for further screening and enrolment.

4.5 Tumour Size Screening

In order to be eligible for inclusion in this study, patients must have disease that is evaluable for 124I-PEG-AVP0458 biodistribution by screening CT scan. Only patients with tumours deemed likely to be assessable by PET by study site nuclear medicine physicians will be eligible for the trial.

5 **Study procedures**

5.1 Screening Visits (Day -21 to -1)

Written informed consent will be obtained. Review study with subject and obtain written informed consent in accordance with TGA requirements and the policies of the responsible HREC. Patients will be informed that they will only be recruited into the Study if their TAG-72 and tumour screenings meet inclusion criteria for the Study.

5.1.1 TAG-72 Screening

The Investigator will send appropriate archived tumour tissue specimen of patient to TissuPath for screening by IHC according to section 4.4. IHC for TAG-72 expression in archived tissue samples may be performed at any time prior to initiating the study.

5.1.2 Tumour Screening (Day -28 to -1)

The Investigator will send CT scan of patient to the Principal Investigator who is a nuclear medicine physician to ascertain the tumour is deemed assessable by PET, according to section 4.5.

5.1.3 All other Screening (Day -21 to -1)

Patients who meet the inclusion criteria for TAG-72 tumour expression will undergo further screening as follows:

- Complete medical history including demographics.
- Complete physical examination
- Vital signs (blood pressure, pulse, respiratory and temperature)
- ECOG (Eastern Cooperative Oncology Group) performance
- 12-lead electrocardiogram
- Full blood profile (CBC and differential)
- Serum biochemistry (electrolytes, urea, creatinine, alkaline phosphatase, bilirubin, albumin, AST, ALT, LDH, calcium, phosphate) and thyroid function levels (TSH)
- Prostate specific antigen (PSA) levels in patients with prostate cancer and CA-125 levels in patients with ovarian cancer.
- Serum pregnancy test for women of child bearing potential
- Concomitant medications. Prescription and non-prescription therapies must be documented. Trade or generic name, indication, quantity administered, route, and dates of administration will be listed. Treatment history will include the 4 weeks prior to the infusion of ¹²⁴I-PEG-AVP0458.

5.2 Baseline prior to Administration of Investigational Product (Day0)

Subjects will attend the study site (Austin Health or Peter MacCallum Cancer Centre) by approximately 8 am.

The following assessments and activities will be undertaken:

- Vital signs (blood pressure, pulse, respiratory and temperature)
- ECOG performance
- Concomitant medications. Prescription and non-prescription therapies must be documented. Trade or generic name, indication, quantity administered, route, and dates of administration will be listed.
- Blood sample taken before infusion of ¹²⁴I-PEG-AVP0458 for assessment of HADA and pharmacokinetics by ELISA and ¹²⁴I counting.
- Administer 10 drops super saturated potassium iodide (SSKI) immediately prior to infusion of ¹²⁴I-PEG-AVP0458 (and twice daily for a total of 10 days).

5.3 Administration of Investigational Product

The appropriate quantities of 124 I-PEG-AVP0458 will be drawn into a syringe with sterile sodium chloride injection and 5% human serum albumin (HSA). The resultant 124 I-PEG-AVP04 in the syringe will be injected into a 100 mL infusion bag of sterile sodium chloride injection and 5% HSA via a sterile 0.2 μ m filter.

Patients will receive 1 mg/m² or 10 mg/m² of ¹²⁴I-PEG-AVP0458 infusion intravenously over approximately 1 hour. Patients will be kept reclined during the infusion and observed for the first four hours after the infusion has been completed.

PEG-AVP-0458 will be labelled with ¹²⁴I in laboratories of the Ludwig Institute of Cancer Research, at Austin Health, under sterile conditions and according to SOPs (see Section 9.3). Following QC testing, the dose of 124 I-PEG-AVP-0458 will be then distributed to the infusion room at the study site for subsequent patient infusion. The criteria for dose escalation and dose selection are provided in Section 5.14.

5.4 Post-Administration of Investigational Product (Day 0)

The following assessments are undertaken:

- Vital signs (blood pressure, pulse, respiratory and temperature) every 15 minutes during the infusion, at completion of infusion, and at 1, 2 and 4 hours after infusion completion. Note: these time points correspond to 2, 3 and 5 hours after commencement of infusion.
- Blood sample taken immediately post infusion, and then at 1, 2 and 4 hours after completion of infusion for assessments of pharmacokinetics by ELISA and ¹²⁴I counting.
- A PET scan is performed approximately 1 hour after infusion, according to the PET Imaging Charter.
- Adverse events, if observed, are recorded, taking special precaution for anaphylaxis, allergic and/or infusion reactions (see Section 5.9.2).

At the end of the assessments (five hours after commencement of infusion), patients may return home if there are no ongoing adverse effects of the infusion.

5.5 Days 1, 2 or 3, 4 or 5, 6 or 7 (Study Visits 1, 2, 3 and 4 post infusion)

Patients return to the Study Site at the appointed time for the following assessments:

- Vital signs (blood pressure, pulse, respiratory and temperature)
- ECOG performance
- Concomitant medications. Prescription and non-prescription therapies must be documented. Trade or generic name, indication, quantity administered, route, and dates of administration will be listed.
- Adverse events
- Blood sample for assessments of pharmacokinetics by ELISA and ¹²⁴I counting
- Blood sample for assessment of HADA on day 6 or 7
- PET scan

Some flexibility is allowed in the schedule (eg. Day 2 or 3, 4 or 5, 6 or 7) to allow for availability of PET/CT scans and weekends. Such flexibility is enabled by the relatively long half-life of the 124I radionuclide and the diabody being studied.

Clinical Study Protocol, Study No AVP0458-01-001, Amendment 4, 23rd October 2012 Page 28 of 46

5.6 Day 14 (± 2) (Study Visit 5)

Patients return to the Study Site at the appointed time for the following assessments:

- Vital signs (blood pressure, pulse, respiratory and temperature)
- ECOG performance
- 12-lead electrocardiogram
- Full blood profile (CBC and differential)
- Serum biochemistry (electrolytes, urea, creatinine, alkaline phosphatase, bilirubin, albumin, AST, ALT, LDH, calcium, phosphate)
- Concomitant medications. Prescription and non-prescription therapies must be documented. Trade or generic name, indication, quantity administered, route, and dates of administration will be listed.
- Adverse events
- Blood sample for assessments of HADA and pharmacokinetics by ELISA and ¹²⁴I counting

5.7 Day 21 (± 2) (Study Visit 6)

Patients return to the Study Site at the appointed time for the following assessments:

- Vital signs (blood pressure, pulse, respiratory and temperature)
- ECOG performance
- Concomitant medications. Prescription and non-prescription therapies must be documented. Trade or generic name, indication, quantity administered, route, and dates of administration will be listed.
- Adverse events
- Blood sample for assessments of HADA and pharmacokinetics by ELISA

5.8 Day 28 (\pm 2) (End of Study Visit 7)

This is the End of Study visit. Patients return to the Study Site at the appointed time for the following assessments:

- Thyroid function levels (TSH)
- Complete physical examination
- Vital signs (blood pressure, pulse, respiratory and temperature)
- ECOG (Eastern Cooperative Oncology Group) performance
- 12-lead electrocardiogram
- Full blood profile (CBC and differential)
- Serum biochemistry (electrolytes, urea, creatinine, alkaline phosphatase, bilirubin, albumin, AST, ALT, LDH, calcium, phosphate)
- Concomitant medications. Prescription and non-prescription therapies must be documented. Trade or generic name, indication, quantity administered, route, and dates of administration will be listed.
- Adverse events
- Blood sample for assessments of HADA and pharmacokinetics by ELISA

At the end of the assessments, the patients will be discharged from the Study Site.

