As this is a first in-human study, a single subject will receive the first dose of ¹²⁴I-PEG-AVP0458. Further dose administration will be sequential within each cohort to mitigate risks of anaphylactic or any other acute unexpected reactions. Administration of doses within a cohort will be staggered by 24 hours, i.e. there will be a period of 24 hours between the first, second and subsequent subjects in a cohort to observe and interpret reactions and adverse events. This time frame is sufficient to exclude any possible acute allergic or anaphylactic reactions to PEG-AVP0458.

After completion of accrual into the first cohort (1 mg/m 2 dose), the Trial Management Committee will review the safety data from these participants before a decision is made to escalate the dose to 10 mg/m 2 .

If no patients entered in the 1^{st} dose group experience a dose-limiting toxicity (DLT), and the Trial Management Committee agree, then the 2^{nd} dose group may commence on the higher dose of 10 mg/m^2 30 days after the last patient on the first dose group has received the 124 I-PEG-AVP0458 infusion. If any one patient in either cohort of 3 patients experiences a DLT, then 3 additional patients will be entered in that dose group. If additional patients are treated in the 1^{st} dose group, all patients entered must have been observed for 30 days before a new patient may receive an infusion in the 2^{nd} dose group. If greater than or equal to two DLTs are observed at a dose, then the MTD is considered to have been exceeded.

If at most, one DLT is observed, the next 3 patients are assigned to the next highest dose. If two or more DLTs are observed, then the MTD is considered to have been exceeded.

A DLT is defined as any of the following events occurring within 30 days of study drug administration:

- Any Grade 2 or greater allergic reaction.
- Any Grade 3 toxicity. Exceptions are: fever; asymptomatic hyperglycemia; hypophosphatemia; nausea, vomiting, or diarrhoea despite the use of optimal supportive medical therapy; leukopenia or thrombocytopenia that revert to baseline within three weeks of occurrence; lymphopenia without other dose-limiting events (eg opportunistic infection).
- Any Grade 4 toxicity.

The 30 days will allow identification and mitigation of the risks of any delayed immunogenic reaction before progressing to a subsequent cohort.

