5.11 Treatment Restrictions

The following therapies may not be used before end of Day 28 of the study:

- Chemotherapeutic or agents with known anti-cancer activity for the disease under study
- Radiation therapy
- Immunotherapy
- Immunosuppressive agents including corticosteroids, except for low dose corticosteroids used for concomitant medical conditions.
- Any other investigational agent.

Topical or inhalational steroids are permitted. Investigators may prescribe concomitant supportive medications or treatments deemed necessary to provide adequate patient care.

All prescription and non-prescription concomitant medications must be recorded in the eCRF, listing generic name, indication, dose and schedule and dates of administration.

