5.13 Patient Evaluability

All patients who receive the infusion of ¹²⁴I-PEG-AVP0458 diabody will be evaluable for safety. Every effort will be made to obtain complete information on all AEs, with particular emphasis on serious AEs, infusional toxicities, and hypersensitivity reactions. Patients will be evaluable for biodistribution and pharmacokinetics assessment if they complete all study procedures up to Visit 4 (Day 6 or 7

visit). Patients will be evaluable for immunogenicity of PEG-AVP0458 if they have completed the Day 28 (±2 days) visit procedures.

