6.1 Safety Evaluation

Safety of ¹²⁴I-PEG-AVP0458 will be determined by the ongoing monitoring of the incidence and intensity of AEs graded using the National Cancer Institute Common Terminology Criteria for Adverse Events (CTCAE) v4.0 (Appendix 2), with special emphasis on DLT events and infusional toxicities. A copy of CTCAE v4.0 also may be downloaded from the Cancer Therapy Evaluation Program home page (http:\\ctep.info.nih.gov).

A DLT is defined as any of the following events occurring within 30 days of study drug administration:

- Any Grade 2 or greater allergic reaction.
- Any Grade 3 toxicity. Exceptions are: fever; asymptomatic hyperglycemia; hypophosphatemia; nausea, vomiting, or diarrhoea despite the use of optimal supportive medical therapy; leukopenia or thrombocytopenia that revert to baseline within three weeks of occurrence; lymphopenia without other dose-limiting events (eg opportunistic infection).
- Any Grade 4 toxicity.

To be dose-limiting, a toxicity must be possibly, probably, or definitely related to the administration of ¹²⁴I-PEG-AVP0458. All DLTs must be discussed with the study Coordinating Principal Investigator.

AEs will be collected after the patient has been enrolled. AEs occurring after signing informed consent but prior to receiving study drug (ie before enrolment) should only be reportable if related to study procedures. All AEs occurring after enrolment must be recorded until 30 days following the end of treatment exposure. Refer to Section 7.2.1. AEs include adverse drug reactions, any unfavourable sign or symptom (related and unrelated), illnesses with onset during the study, or exacerbations of pre-existing illnesses or conditions. Progression of the patient's malignancy should not be considered an AE, unless, in the Investigator's opinion, study treatment resulted in an exacerbation of the patient's condition. Exceptions are if disease progression results in death or hospitalization while on study or within 30 days of the last dose. If either occurs, progressive disease will be reported as a SAE (see Section 8.2.2) and will also be documented on an AE eCRF. All observed or volunteered AEs, regardless of treatment group or suspected causal relationship to study drug, will be recorded on the AE eCRF.

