7.2.2 Serious Adverse Events (SAEs)

After becoming aware that an SAE has occurred, all sites must report it to the Sponsor or designee within 24 hours of awareness of the event, regardless of suspected relationship to study drug. Sites will be provided with contact information for SAE reporting before enrolling their first patient.

The initial report should include at minimum the following information: patient number and initials, sex, age; event term; and Investigator's preliminary assessment of causality. Follow-up information including causality, severity, outcome, action taken, and concomitant medications should be communicated to the Sponsor immediately.

Any SAE or death must be reported immediately regardless of the circumstances or suspected cause if it occurs or comes to the attention of the Investigator any time a patient is on study (as soon as the informed consent has been signed) or within 30 days of study drug

Clinical Study Protocol, Study No AVP0458-01-001, Amendment 4, 23rd October 2012 Page 37 of 46

administration. Any SAE or death occurring more than 30 days after drug administration must be reported if a causal relationship to study drug is suspected.

It is the Investigator's responsibility to notify the Ethics Committees of all SAEs that occur at his or her site.

Study site personnel must fax the completed SAE form(s) within one working day to Medpace Serious Adverse Event Reporting [contact]. Attach a photocopy of all examinations carried out and the dates on which these examinations were performed. For laboratory results, include the normal ranges.

Type of Event	Reporting Time to	Reporting Time to TGA	Type of Report
	Designee by Site		
Fatal or Life-threatening	Within 24 hours	Within 7 calendar days	Initial report
	Within 7 days	Within 8 additional	Complete report
		calendar days	
All Other Serious	Within 24 hours		Initial report on SAE
			Report – Form
	Within 7 working days	Within 15 calendar days	Updated information
			on the original SAE
			Report - Form
Non-serious	Per eCRF submission		AE Report - Form
	procedure		

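### DLTs and AEs count to Day 30, but the last scheduled contact is the Day 28 (±2) visit, so late events rely on unscheduled reporting, and the ban on other therapy ends 2 days early

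*Protocol*

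**What the plan says.** **The 30-day clock.** Section 3.1 states "A DLT is defined as any of the following events occurring within 30 days of study drug administration", and Section 6.1 repeats the definition. Section 3.1 also gives a reason for the length: "The 30 days will allow identification and mitigation of the risks of any delayed immunogenic reaction before progressing to a subsequent cohort". Section 6.1 sets AE recording to match: "All AEs occurring after enrolment must be recorded until 30 days following the end of treatment exposure". With one infusion on Day 0, that means Day 30.

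Under Sections 3.1 and 5.10, with no DLT in dose group 1, dose group 2 may open 30 days after the last group 1 infusion. Section 3.1 adds that the Trial Management Committee must agree. If group 1 is expanded, "all patients entered must have been observed for 30 days before a new patient may receive an infusion" in group 2.

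**The 28-day clock.** The last column of the Schedule of Events is the End of Study visit at Day 28 (±2). Section 5.8 describes that visit and closes with "At the end of the assessments, the patients will be discharged from the Study Site". Section 5.13 makes a patient evaluable for immunogenicity "if they have completed the Day 28 (±2 days) visit procedures". Section 8.3 defines the evaluable population by 4 weeks of scheduled assessments. Section 5.11 opens its list of barred treatments with "The following therapies may not be used before end of Day 28 of the study". Neither the Schedule nor Section 5 provides a visit or telephone call after Visit 7.

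**The concern.** The protocol runs on two clocks that do not meet. DLT status and escalation use 30 days; visits and treatment restrictions use 28. The days that fall between them are at the end of the window, and Section 3.1 justifies the length of that window by delayed immunogenic reactions.

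Two things are at stake.

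- **Ascertainment.** After the last visit, the site learns of an event only if the patient or another carer reports it unprompted. A non-serious DLT could go unheard at that point; an allergic reaction of Grade 2 counts as a DLT under Section 3.1. With three patients per cohort and a tenfold step from 1 to 10 mg/m² in a first-in-human study, one missed DLT changes the action from expanding the cohort to escalating.
- **Attribution.** Section 6.1 requires a DLT to be at least possibly related to the study drug. If chemotherapy, radiotherapy, immunotherapy or another investigational agent starts on Day 29, judging an event on Day 29 or 30 is harder.

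**Working it through.** **Inputs.** DLT window: 30 days (Sections 3.1 and 6.1). Infusion: Day 0. Last visit: Day 26 to Day 30 (Schedule; Section 5.8). Restriction on other therapy: to the end of Day 28 (Section 5.11). Patients: 12–18 (Section 3.2), which is reproduced by 3 + 3 + 6 = 12 and 6 + 6 + 6 = 18.

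**Step 1: days without a scheduled assessment** = 30 − day of last visit.

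| Last visit | Gap (days) | Share of window |
|---|---|---|
| Day 26 | 30 − 26 = 4 | 4/30 = 13% |
| Day 28 (nominal) | 30 − 28 = 2 | 2/30 = 7% |
| Day 30 | 30 − 30 = 0 | 0% |

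**Step 2: days of the DLT window open to other therapy** = 30 − 28 = 2 (Days 29 and 30).

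**Step 3: does anything else in the protocol confirm status at Day 30?** With no DLT in the cohort, the 30-day wait is counted from the last infusion and requires no contact at its end. Section 3.1 places the committee's safety review after accrual into the first cohort is complete; it does not tie the review to a recorded 30-day status for each patient. The rule for an expanded cohort does ask for 30 days of observation, but the Schedule provides a contact that late only if the visit falls on Day 30.

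**Step 4: how far could escalation move?** This is an upper-end illustration, not an estimate. Let p be the true 30-day DLT risk. The protocol gives none, so 0.10 to 0.40 is assumed. Dose group 1 escalates with 0 of 3 DLTs, or with 1 of 3 followed by 0 of 3:

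P(escalate) = (1 − p)³ + 3p(1 − p)² × (1 − p)³

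Assume a constant hazard over 30 days and that every DLT in the last g days is missed. The risk that is seen is then p_obs = 1 − (1 − p)^((30 − g)/30), which replaces p in the formula.

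Example at p = 0.20: 0.8³ + 3 × 0.2 × 0.8² × 0.8³ = 0.5120 + 0.1966 = 0.7086. With g = 2, p_obs = 1 − 0.8^(28/30) = 0.1880 and P(escalate) = 0.7345.

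| Assumed p | No gap | 2-day gap | 4-day gap | Rise (percentage points) |
|---|---|---|---|---|
| 0.10 | 0.9061 | 0.9164 | 0.9262 | 1.0 to 2.0 |
| 0.20 | 0.7086 | 0.7345 | 0.7604 | 2.6 to 5.2 |
| 0.30 | 0.4943 | 0.5292 | 0.5657 | 3.5 to 7.1 |
| 0.40 | 0.3093 | 0.3441 | 0.3823 | 3.5 to 7.3 |

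**The case against.** The strongest reply is that the end of the window is not abandoned.

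- **Recording and reporting continue.** AE recording runs to Day 30 by Section 6.1. Section 7.2.2 requires SAEs and deaths within 30 days of the drug to be reported immediately, and goes further: "Any SAE or death occurring more than 30 days after drug administration must be reported if a causal relationship to study drug is suspected". The escalation wait also runs the full 30 days. The sentence on discharge in Section 5.8 describes leaving the site after the visit and does not end these duties. All of this stands. A reader might infer that the last days are unobserved, or that patients are declared DLT-free with no information; the text does not support either. What is missing is a scheduled contact.
- **Bias is conditional.** A reader might also infer that the DLT count is biased downward. That follows only if late events go unreported. Many DLTs would be symptomatic or serious and would probably come to light. This stands too; the likelier losses are non-serious events and silent laboratory changes.
- **Attribution leans the other way.** An event that is only possibly related still counts as a DLT under Section 6.1, so new therapy need not remove it from the count. Nothing says that other therapy will start on Day 29. This reduces the attribution point to a possible complication.
- **The gap is short.** It is 2 days at the nominal visit and may be 0. Section 3.1 does not expect a maximum tolerated dose to be found, and anti-diabody antibodies are measured up to the Day 28 visit. This limits the size of the problem. It does not explain why the protocol requires 30 days of observation and schedules contacts only to Day 28 (±2).

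**Conclusion.** The point holds as an internal mismatch of modest size. A compliant patient has no scheduled assessment for the last 0 to 4 days of a 30-day window on which escalation depends (2 days at the nominal visit), and the restriction on other anti-cancer therapy stops 2 days before that window closes. These gaps follow from the dates alone.

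Any effect on escalation depends on assumptions. With constant hazard and every late DLT missed, the chance of escalating from dose group 1 rises by about 1 to 7 percentage points over assumed risks of 0.10 to 0.40. Because reporting duties continue to Day 30, the real effect should be smaller. The direction, if there is an effect, is towards escalating. It is worth correcting because the remedy is cheap and the decision it protects is a tenfold first-in-human dose step.

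**What to change.** 1. Add to the Schedule of Events and Section 5.8 one AE and concomitant-therapy contact for each patient on or after Day 30. A telephone call is enough for symptoms and new treatment. It would not detect toxicity visible only in laboratory tests, and the protocol should acknowledge that limit.
2. State in Sections 3.1 and 5.10 that the Trial Management Committee makes the escalation decision only once that contact is recorded for every patient in the cohort.
3. The sponsor must reconcile the end of the Section 5.11 restriction with the 30-day DLT window in Sections 3.1 and 6.1. Which date should govern is a clinical decision for the sponsor.

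The cost is 12–18 short calls, one per patient, an amendment to the sections named, and possibly a day or two before dose group 2 opens while the last call is logged. With the contact in place, no part of the DLT window lies beyond the last scheduled contact.
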